5. SELECTION OF STUDY POPULATION

5.1. NUMBER OF SUBJECTS

Twelve (12) subjects will be selected for inclusion in the study. A subject who withdraws subsequent to the pre-trial evaluations but before the application of the investigational product will not be considered as a drop-out and will not be included in the database. Standbys should be recruited and be available to replace a subject who withdraws prior to the first drug application. Drop-outs will not be replaced. Justification for the number of subjects is presented in section 9.4.

An effort will be made to include similar proportions of males and females in the study.

5.2. INCLUSION CRITERIA

Volunteers meeting all of the following criteria will be considered for enrollment in the study. A signed copy of the informed consent form will be provided to each subject.

- 1. Availability for the entire study
- 2. Motivated volunteer and absence of intellectual problems likely to limit the validity of consent to participate in the study or the compliance with protocol requirements; ability to cooperate adequately; ability to understand and observe the instructions of the physician or designee
- 3. Healthy adult volunteer
- 4. A female volunteer must meet one of the following criteria:
 - a) Participant is of childbearing potential and agrees to use one of the accepted contraceptive regimens from at least 28 days prior to the first administration of the study drug, during the study and for at least 30 days after the last dose of the study drug. An acceptable method of contraception includes one of the following:
 - Abstinence from heterosexual intercourse
 - Systemic contraceptives (birth control pills, injectable/implant/insertable hormonal birth control products, transdermal patch)

- Intrauterine device (with or without hormones)
- Condom with spermicide

or

b) Participant is of non-childbearing potential, defined as surgically sterile (i.e. has undergone complete hysterectomy, bilateral oophorectomy, or tubal ligation) or in a menopausal state (at least 1 year without menses)

- 5. Volunteer aged ≥ 18 and ≤ 60 years (inclusive)
- 6. Volunteer with a BMI greater than or equal to 19.00 kg/m^2 and below or equal to 32.00 kg/m^2
- 7. Volunteer with a body weight \geq 55 kg
- 8. Non- or ex-smokers; an ex-smoker being defined as someone who completely stopped smoking for at least 3 months before study day 1
- 9. Clinical laboratory values within the laboratory's stated normal range; if not within this range, they must be without any clinical significance as determined by the medical investigator
- 10. Have no clinically significant diseases captured in the medical history or evidence of clinically significant findings on physical examination and/or clinical laboratory evaluations (hematology, general biochemistry, and urinalysis) as determined by the medical investigator
- 11. Willingness to adhere to the protocol requirements as evidenced by the informed consent form (ICF) duly read, signed and dated by the volunteer

The informed consent form must be signed by all volunteers prior to their participation in the study.

5.3. EXCLUSION CRITERIA

Volunteers presenting any of the following will not be included in the study:

- 1. Females who are pregnant or are lactating
- 2. Seated pulse rate less than 45 Beats per Minute (bpm) or more than 100 bpm at screening, unless deemed non-significant by the medical investigator.
- 3. Seated blood pressure below 100/60 mmHg or higher than 140/90 mmHg at screening, unless deemed non- significant by the medical investigator

- 4. History of significant hypersensitivity to chlorhexidine or any related products (including excipients of the formulations) as well as severe hypersensitivity reactions (like angioedema) to any drugs
- 5. Presence of significant gastrointestinal, liver or kidney disease, or any other conditions known to interfere with the absorption, distribution, metabolism or excretion of drugs or known to potentiate or predispose to undesired effects
- 6. History of significant gastrointestinal, liver or kidney disease that may affect drug bioavailability
- 7. Presence of significant cardiovascular, pulmonary, hematologic, neurological, psychiatric, endocrine, immunologic or dermatologic disease
- 8. Volunteers who have presence of a skin condition, excessive hair, scar tissue, tattoo, piercing, skin coloration, open sores or sunburn at the application site that would interfere with application, or reactions to drug
- 9. Any method of hair removal (e.g. waxing, shaving, epilating, laser) at the application site 7 days prior to the first application as well as hair removal with tweezers at the application site 58 hours prior to the first application
- 10. Sunbathing and using tanning beds at the application site 7 days prior to the first application
- 11. Use of topical product containing medication for application (including creams, lotions, ointments, gels, topical solutions, patches; including salicylate-based topical creams or ointments) at the application site 14 days prior to the first application
- 12. Use of topical product without medication (including make-up, sunscreen, creams, lotions, powders, alcohol) at the application site 7 days prior the first application
- 13. Use of oral acetylsalicylic acid (ASA) and salicylic acid or any oral product containing ASA or salicylic acid, in the previous 7 days before study day 1
- 14. History of or disposition to seizures, state of confusion, clinically relevant psychiatric diseases
- 15. Maintenance therapy with any drug or significant history of drug dependency or alcohol abuse (> 3 units of alcohol per day, intake of excessive alcohol, acute or chronic)
- 16. Any clinically significant illness in the previous 28 days before study day 1

- 17. Use of any enzyme-modifying drugs, including strong inhibitors of cytochrome P450 (CYP) enzymes (such as cimetidine, fluoxetine, quinidine, erythromycin, ciprofloxacin, fluconazole, ketoconazole, diltiazem and HIV antivirals) and strong inducers of CYP enzymes (such as barbiturates, carbamazepine, glucocorticoids, phenytoin, rifampin and St John's Wort), in the previous 28 days before study day 1
- 18. Any history of tuberculosis and/or prophylaxis for tuberculosis
- 19. Positive screening of alcohol, and/or drugs of abuse
- 20. Positive results from the hepatitis serology, except for vaccinated subjects or subjects with past but resolved hepatitis, at screening.
- 21. Positive results from the HIV serology at screening
- 22. Volunteers who have already been included in one group of this clinical study.
- 23. Volunteers who took chlorhexidine in the previous 28 days before study day 1
- 24. Volunteers who took an Investigational Product in the previous 28 days before study day 1
- 25. Volunteers who donated plasma in the previous 14 days before study day 1
- 26. Donation of 1 blood donation unit (American Red Cross, etc.) in the previous 56 days before study day 1

5.4. CRITERIA FOR REMOVAL OF A SUBJECT

Subjects will be allowed to discontinue their participation in the study at any time.

Subjects will be discontinued from the clinical study and/or period for any of the following reasons:

- 1. Use of oral ASA and salicylic acid or any oral product containing ASA or salicylic acid during the study
- 2. Sunburn, sunbathing and/or use of topical medication/product at the application site during the study
- 3. Hair removal at the application site during the study
- 4. Presence of any skin condition that would interfere with the application of the study medication
- 5. Females who are pregnant according to a positive pregnancy test
- 6. Clinically significant laboratory values before each period, as judged by the Principal Investigator or designee
- 7. Positive screening of alcohol and/or drugs of abuse

Furthermore, participation in the clinical study and/or period could be discontinued by the physician in charge of the study or by the sponsor for any of the following reasons:

- 1. Adverse events;
- 2. Significant protocol violation;
- 3. Difficulties with blood collection;
- 4. The subject is uncooperative during the study

The PK facility can, with sponsor's approval, also remove a subject from the study due to an unanticipated event that could result in an inadequately characterized pharmacokinetic profile, such as a missed blood draw, an adverse event, meal deviations or concomitant medications.

Details of reasons for removal of subjects will be recorded, reported to the sponsor and documented in the clinical study report.

5.5. **RESTRICTIONS**

Each subject will be questioned on the specific points listed below prior to each treatment. If a subject admits non-compliance with any of these restrictions, the Principal Investigator (or designee) and/or the sponsor will decide whether the subject will be permitted to remain in the study. Non-compliance with these restrictions will be noted.

5.5.1. Medications

In addition to the drugs prohibited as per the exclusion criteria, subjects will be requested to abstain from taking any other prescription medications used with the intention to treat a condition for 28 days prior to the first treatment and during the study, unless judged differently by the Principal Investigator or designee.

Systemic contraceptives and hormone replacement therapy will be permitted.

Subjects will also be requested to abstain from taking any over-the-counter (OTC) products for 7 days prior to the first treatment and during the study. They will be specifically reminded that this includes cold preparations, non-steroidal anti-inflammatory drugs (NSAIDs), vitamins and natural products used for therapeutic benefits and antacid preparations.

Vitamins used as nutritional supplements in non-therapeutic doses (as judged by the Principal Investigator or designee) may be accepted, but they must be stopped at least 48 hours prior to the first treatment and during the study.

Subjects will be instructed not to apply topical products without medication (including make-up, sunscreen, creams, lotions, powders, alcohol) to the skin area where the drug will be applied from 7 days prior to the first treatment until the end of the study.

Subjects will be instructed not to apply topical product containing medication for application (including creams, lotions, ointments, gels, topical solutions, patches; including salicylate-based topical creams or ointments) to the skin area where the drug will be applied from 14 days prior to the first treatment until the end of the study.

If a medication (including OTC) other than those specified in the protocol is used after the first treatment or at any time before the end of the study, the Principal Investigator or designee and/or the sponsor will decide whether the subject will be permitted to remain in the study, depending on the drug used, the time of drug intake, etc. The drug and dose will be noted.

5.5.2. Alcohol

Subjects will be requested to abstain from alcohol for 58 hours prior to each treatment and during each study period. Throughout the study in case of any doubt about alcohol consumption, a test for alcohol may be performed if requested by the physician.

5.5.3. Xanthines

Subjects will be requested to avoid food or beverages containing xanthines (i.e. tea, coffee, cola drinks, energy drinks or chocolate) for 58 hours prior to each treatment and during each study period.

5.5.4. Fluids

Fluid intake other than water will be controlled for each housing period and for all subjects. Water will be provided *ad libitum* during the housing periods.

Non-carbonated, non-xanthine and non-grapefruit fluids will be provided during the housing periods.

5.5.5. Food

Food will be controlled and standardized for all subjects for each housing period. Meals and snacks will be served at appropriate times.

5.5.6. Grapefruit, Seville Oranges, poppy-seed and pomelo-containing beverages and food

Subjects will be instructed to avoid food or beverages containing grapefruit, Seville oranges and/or pomelo for 7 days prior to the first treatment and during the study.

Food or beverages containing poppy-seeds should also be avoided for 36 hours prior to the first treatment and during the study.

5.5.7. Posture and physical activities

Subjects will remain seated for at least the first 4 hours following each treatment. However, should adverse events occur, subjects may be placed in an appropriate position. During this interval subjects will be permitted, under supervision, to leave their seats for brief periods, e.g. to use the washroom facilities or for blood sampling (if necessary). After this 4-hour period, subjects may get up, but only under supervision. Subjects will not engage in strenuous activity at any time during the housing periods.

5.5.8. Contraceptive regimen throughout the study

Female volunteers of childbearing potential will have to take appropriate measures to prevent pregnancy for at least 28 days prior to the first treatment, during the study and for at least 30 days after the last treatment, as described in section 5.2.

5.5.9. Other Activities

Subjects will be instructed that sunbathing and using tanning beds at the area intended for drug application is not allowed from 7 days prior to the first treatment and throughout the study in order to avoid sunburn at the application site.

Subjects will be instructed not to shave, wax, epilate or laser (for hair removal) the skin area where the drug will be applied from 7 days prior to the first treatment until the end of the study. Moreover, subjects will be instructed not to remove hair with tweezers to the skin area where the drug will be applied for 58 hours prior to the first treatment until the end of the study.

In each study period, subjects will be required to not take a shower for 2 hours prior to the treatment until departure from the clinical site.

6. CLINICAL PROCEDURES

Unless otherwise stated in this protocol, SOPs of the clinical site, which are available for all activities relevant to the quality of the study, will be followed during this study. The different parts of this study are summarized in Table 1 and explained in the following sections.

6.1. DESCRIPTION OF STUDY DAYS

6.1.1. Pre-trial evaluation

Potential study volunteers will be examined before the start of the study to determine their eligibility for participation. These tests are to be conducted no more than 28 days before the start of the study. The following examinations will be performed:

6.1.1.1. Medical history

The medical history will include evaluation of ears, nose, throat and any ophthalmological, cardiovascular, respiratory, musculoskeletal, gastrointestinal, genitourinary, neurological, endocrine, psychiatric, immunological or allergic, dermatological, hematological, family history disorder or disease.

6.1.1.2. Physical examination

The physical examination will include measurement of vital signs (blood pressure, pulse rate, respiratory rate and body temperature) and a review of the following: head and neck, heart, lungs, abdomen and general appearance. Skin examination at the application sites will be performed.

Demographic data (age, gender, race, ethnicity, body weight adjusted for indoor clothing, height, BMI), and alcohol and smoking habits will be recorded.

6.1.1.3. Laboratory tests

- General Biochemistry: Sodium, potassium, chloride, glucose, blood urea nitrogen (BUN), creatinine, bilirubin total, alkaline phosphatase, AST, ALT, albumin, calcium, carbon dioxide, inorganic phosphate, magnesium, total protein and uric acid
- Hematology: White cell count with differential (absolute values of neutrophil, lymphocyte, monocyte, eosinophil, and

basophil), red cell count, hemoglobin, hematocrit, mean corpuscular volume (MCV), and platelets count

Urinalysis: Color, clarity, specific gravity, pH, leukocyte, protein, glucose, ketones, bilirubin, blood, nitrite, urobilinogen. Microscopic examination will only be performed if the dipstick test is outside of the reference range for leukocyte, blood, nitrite or protein

6.1.1.4. Other laboratory tests

Serology: HIV Ag/Ab Combo, Hepatitis B (HBsAg (B)) and Hepatitis C (HCV (C))
Drug Screen: Alcohol, amphetamines, barbiturates, cannabinoids, cocaine, opiates, oxycodone and benzodiazepine

A pregnancy test will be performed on female subjects.

6.1.1.5. Other tests

Additional laboratory tests may be also performed by the medical laboratory as part of larger standard tests panels although not required for the subject's safety. All test results will be assessed by physician for clinical significance. Only test results required by the protocol and/or abnormal results will be entered in the clinical database and reported in the Clinical Study Report, based on the report requirement.

6.1.2. Study days

The following procedures will be applied for each period of the study:

Subjects will be admitted to the clinical site up until at least 10 hours prior to drug administration.

Screening of alcohol and drugs of abuse will be performed at the subjects' arrival, prior to drug application.

A pregnancy test will be performed at the female subject's arrival, prior to drug application.

General biochemistry tests will be performed before each period of the study.

The first baseline blood sample will be collected 10 hours prior to each treatment (T = -10.00). After a supervised overnight fast, the subjects will be awakened, vital signs (blood pressure, pulse rate, respiratory rate and body temperature) will be measured, visual skin evaluation at the application site will be performed and the 2 other baseline blood samples (T= -2.00 and -0.50) will be collected. *Pre-dose vital signs should be done within 120 minutes of drug application*.

Serial blood sampling will follow drug administration (details in section 6.2.1).

Vital signs (blood pressure and pulse rate) will be assessed twice after treatment (details in section 6.3).

Visual skin evaluation at the application site will be performed several times after treatment (details in section 6.3).

Subjects may leave the clinical site at least 24 hours after treatment. However, they will be advised to stay at the clinical site, if judged necessary by the physician in charge, for safety reasons. A card identifying the medication 'Chlorhexidine Gluconate' will be distributed to all subjects prior to departure from the clinical site in period 1. This card is given to subjects in order for them to inform the hospital / doctors they are participating in a clinical trial in case of a medical emergency.

6.1.2.1. Drug administration procedure

ReadyPrep[®] CHG Application (Treatment-1 and Treatment-2):

In two Treatment-1 and -2, a single topical application of ReadyPrep[®] CHG will be done on either the abdomen (surface area of approximately 5 x 5 inches) or the groin (surface area of approximately 5 x 2 inches) according to the randomization scheme.

The drug will be applied to a clean, dry, non-irritated, normal skin area. Possible hairs will be removed by means of scissors (no shaving) on the morning of dosing.

Approximately 30 minutes prior to any application, the site should be gently washed with room temperature water and dried without rubbing or heavy pressure with a gauze or similar cotton soft material. The application site must be allowed to dry for at least 15 minutes before drug application. After drying, the application site will be marked for dose location.

The topical application of ReadyPrep[®] CHG will consist of a 3-minute vigorous rub followed by a 1 minute dry time at the application site. The

1-minute dry time will be air drying without dabbing or rubbing. The time of dosing will be defined as the start time of the drug application on the skin.

Control Treatment (Treatment-3):

In Treatment-3, the same procedures as Treatment-1 and -2 will be performed, but without the topical application of ReadyPrep® CHG or placebo (no placebo ReadyPrep[®] cloth will be provided or used). Therefore, approximately 30 minutes prior, the site should be gently washed with room temperature water and dried without rubbing or heavy pressure with a gauze or similar cotton soft material. The application site must be allowed to dry for at least 15 minutes and after drying, the skin site will be marked. Subjects should be placed in the same position, for the same length of time, in the same area as they would be dosed.

The physician will remain at the clinical site for at least the first 4 hours following each treatment and will remain available at all times during the entire period of the study.

6.1.3. End of the study

The following poststudy tests will be performed at the end of the study.

For subjects whose participation in this clinical study is discontinued during the course of the trial, every effort will be made to perform the poststudy tests as soon as possible after discontinuation.

6.1.3.1. Physical Examination

The physical examination will include measurement of vital signs (blood pressure, pulse rate, respiratory rate and body temperature) and a review of the following: head and neck, heart, lungs, abdomen and general appearance

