10.11. PREMATURE TERMINATION OR SUSPENSION OF A STUDY	
10.12. Adherence to protocol	
11. REFERENCES	
APPENDIX 1: AMENDMENT 01	46

LIST OF TABLES

Table 1. Study Design and Schedule of Assessments	. 43
Table 2. Blood Sampling Schedule	. 44
Table 3. Pharmacokinetic Parameters	. 45

STUDY SYNOPSIS

Title of Study :	Single Dose Pharmacokinetic Study to Assess the Systemic Exposure of Chlorhexidine from ReadyPrep [®] CHG (2% Chlorhexidine Gluconate Cloth)	
Phase:	Phase I study	
Investigational Pro	duct : ReadyPrep [®] CHG (2% Chlorhexidine Gluconate Cloth) Manufacturer: Medline Industries, Inc., USA	
Treatments:	Treatment-1: Abdominal application of ReadyPrep [®] CHG	
	Treatment-2: Groin application of ReadyPrep [®] CHG	
	Treatment-3: Control treatment with no application	
Objective :	The primary objective of this study is to demonstrate that no or negligible systemic exposure occurs after a single topical application of ReadyPrep [®] CHG.	
	The secondary objective of this study is to determine the safety and tolerability of a single topical application of ReadyPrep [®] CHG in healthy volunteers after a single topical application.	
Study Design:	Single center, randomized, single dose, laboratory-blinded, 3-period, 3- sequence, crossover design.	
Subjects :	Twelve (12) subjects will be included in the study	
Main Inclusion Cri	teria: Male and female volunteers, non- or ex-smokers, ≥ 18 and ≤ 60 years of age (inclusive) with a body mass index (BMI) greater than or equal to 19.00 and below or equal to 32.00 kg/m ² and a body weight ≥ 55 kg will be selected according to the inclusion and exclusion criteria. They will be healthy according to medical history, complete physical examination (including vital signs and skin examination) and laboratory tests (general biochemistry, hematology, urinalysis) including negative Human Immunodeficiency Virus (HIV), Hepatitis B and Hepatitis C tests as well as negative drug screening of alcohol, and drugs of abuse. For female subjects, a pregnancy test must be negative.	
Administration:	In Treatment-1 and -2, a single topical application of ReadyPrep [®] CHG consisting of a 3-minute vigorous rub followed by a 1 minute dry time will be done at the application site. In one study period, the application site	

will be the abdomen (surface area of approximately 5 x 5 inches) and in the other study period, the application site will be the groin (surface area of approximately 5×2 inches).

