Treatment-3 will consist of a control treatment where the same procedures as Treatment-1 and -2 will be performed, but without the topical application of ReadyPrep[®] CHG.

Subjects will remain seated for at least the first 4 hours following each treatment.

- Blood Sampling: In each study period, 12 blood samples will be collected. Baseline levels will be assessed before each treatment. For baseline assessment, 3 blood samples will be collected prior to each treatment while the others will be collected up to 24 hours after each treatment.
- **Housing**: From at least 10 hours prior to each treatment until 24 hours following each treatment.
- **Wash-out**: The treatment will be separated by at least 7 calendar days.
- **Tests during study**: Drug and alcohol screening will be performed before each period of the study.

For female subjects, a pregnancy test will be performed before each period of the study.

General biochemistry tests will be performed before each period of the study.

Vital signs will be measured prior to and approximately 12 and 24 hours following each treatment.

Visual skin evaluation at the application site will be performed prior to and approximately 4, 8 and 24 hours after treatment.

Poststudy Tests: Hematology, general biochemistry tests (including a pregnancy test for female subjects) and urinalysis will be repeated at the end of the study.

A complete physical examination (including vital signs) will be performed.

Safety data: Safety will be evaluated through the assessment of adverse events (AE), laboratory tests, vital signs, visual skin evaluation and physical examination.

Bioanalysis: Chlorhexidine plasma concentrations will be measured by a validated bioanalytical method.

- **Pharmacokinetics:** In the event that chlorhexidine levels are measurable, the pharmacokinetic parameters will be estimated with and without baseline adjustment. Main absorption and disposition parameters will be assessed using a non-compartmental approach with a log-linear terminal phase assumption. Trapezoidal rule will be used to estimate the area under the curve. The pharmacokinetic parameters of interest will be C_{max} , AUC_{0-T} and AUC_{0- ∞}. Other parameters including T_{max} , AUC_{0-T/ ∞}, λ_{Z_c} , T_{half_c} Cl/F and V_d /F will be calculated and provided for information purposes only.
- **Statistics**: No statistical analysis will be performed.

LIST OF ABBREVIATIONS AND DEFINITION OF TERMS

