1. INTRODUCTION

Chlorhexidine [CHD; 1,1'-hexamethylenebis[5-(4-chlorophenyl) biguanide]] has a wide spectrum of bactericidal and antiviral activity and is a common ingredient in various formulations ranging from skin disinfectants in healthcare products to antiplaque agents in dentistry. The presence of two symmetrically positioned basic chlorophenyl guanide groups attached to a lipophilic hexamethylene chain aid in rapid absorption through the outer bacterial cell wall, causing irreversible bacterial membrane injury, cytoplasmic leakage, and enzyme inhibition. Chlorhexidine exists as various forms of salts: diacetate, dihydrochloride, or digluconate, mainly differing by their solubilizing abilities in aqueous or oily media. Chlorhexidine digluconate (or gluconate), as most soluble in water or alcohol, is the most used form in topical dermatology or cosmetic preparations.^{1,2}

As chlorhexidine is not significantly absorbed through intact skin³ no systemic adverse events are expected. However, skin reaction could occur.

ReadyPrep[®] CHG is composed of 2% chlorhexidine gluconate (CHG) solution on a single fiber, polyester cloth. Each cloth contains 500 mg CHG. The sponsor is developing ReadyPrep[®] CHG (2% Chlorhexidine Gluconate Cloth) for patient preoperative skin preparation.

In order to better understand and control for the presence of chlorhexidine in the environment, baseline levels will be assessed in each study period and a control treatment arm will be included.

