6.1.3.4. Other tests

No other tests will be performed at the end of the study.

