6.3.3. Visual skin evaluation

Visual skin evaluation of the application site will be performed by the physician in charge or designee as follows:

Application site verification (for redness, markings, scars, etc.) will be documented prior to and approximately 4, 8 and 24 hours after each treatment.

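### The exit examination omits the application-site skin check made at screening, so 16 of the 24 active applications have no assured skin inspection after about 24 hours

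*Protocol*

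**What the plan says.** - **Screening.** Protocol section 6.1.1.2 lists vital signs and a set of body regions, then adds: "Skin examination at the application sites will be performed". The synopsis agrees, describing a "complete physical examination (including vital signs and skin examination").
- **End of study.** Section 6.1.3.1 gives vital signs and "a review of the following: head and neck, heart, lungs, abdomen and general appearance". The sentence on the skin is not repeated. The synopsis, under poststudy tests, says: "A complete physical examination (including vital signs) will be performed". Section 6.1.3.4 adds: "No other tests will be performed at the end of the study".
- **Early withdrawal.** Section 6.1.3 applies the same list: "every effort will be made to perform the poststudy tests as soon as possible after discontinuation".
- **Within each period.** Under section 6.3.3 the condition of the application site "will be documented prior to and approximately 4, 8 and 24 hours after each treatment". The site is named in the singular, and nothing asks for a look at a site treated in an earlier period.
- **Expected effect.** The Introduction expects no systemic adverse events, then says: "However, skin reaction could occur". Safety and tolerability form the secondary objective (section 2).

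**The concern.** The plan takes a baseline of the skin at both sites and has no matching observation at exit. The exit visit repeats biochemistry, hematology and urinalysis, although no systemic effect is expected, but does not require a look at the skin, where an effect is expected. The two active treatments go on different sites in different periods, so the checks of a later period do not automatically revisit the earlier site.

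What is at stake is the evidence for tolerability. As written, a reaction that appears after 24 hours, or one seen at 24 hours that persists, is recorded only if the subject reports it or staff happen to notice it. A statement that the product was well tolerated on the skin would then rest on inspection over about 24 hours plus self-report. That is avoidable, since subjects come back to the site anyway.

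**Working it through.** **Inputs.** Sequence table and group sizes (section 4: three sequences, n = 4 each); treatment on Days 1, 8 and 15 and End of Study on Day 16 (Table 1); skin checks before treatment and up to about 24 hours (section 6.3.3); content of the two physical examinations (sections 6.1.1.2 and 6.1.3.1).

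**Calendar check.** Day -1 to Day 16 without a Day 0 is 1 + 16 = 17 days. This matches the approximately 17 days in section 4 and places End of Study on the day of the Period 3 24-hour check.

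**Active applications.** 12 subjects × 2 active periods = 24. The interval to exit is 16 minus the treatment day.

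| Sequence | Period | Site | Treated | 24 h check | Days to exit | n |
|---|---|---|---|---|---|---|
| 1 | 1 | abdomen | Day 1 | Day 2 | 15 | 4 |
| 2 | 1 | groin | Day 1 | Day 2 | 15 | 4 |
| 1 | 2 | groin | Day 8 | Day 9 | 8 | 4 |
| 3 | 2 | abdomen | Day 8 | Day 9 | 8 | 4 |
| 2 | 3 | abdomen | Day 15 | Day 16 | 1 | 4 |
| 3 | 3 | groin | Day 15 | Day 16 | 1 | 4 |

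- Period 3: 4 + 4 = 8 applications. Exit and the 24-hour check fall on the same day, so nothing is lost in completers.
- Periods 1 and 2: 24 − 8 = 16 applications (16/24 = 67%), of which 8 are abdominal and 8 are groin.
- No site receives the product twice in the same subject, so a later active period never brings the earlier site back under scheduled inspection.

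**Could the control period close the gap?** It follows an active treatment in Sequences 1 (Period 3) and 2 (Period 2). Section 6.1.2.1 has a site washed and marked in the control period but does not say which one.

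- Control site is the groin: the 8 groin applications in Sequences 1 and 2 are seen again. The 8 abdominal ones (Sequences 1 and 3) are not.
- Control site is the abdomen: only the 4 abdominal applications in Sequence 1 are seen again, and 16 − 4 = 12 are not.
- Both sites are inspected: 12 are seen again. The 4 abdominal applications in Sequence 3 are not, because Period 3 there treats the groin.

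On any of these readings, between 4 and 12 of the 16 have no later scheduled skin evaluation. Since the text fixes none of them, a later evaluation is assured for none of the 16.

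**What the exit examination adds.** The abdomen is on its list and the groin is not. The 8 abdominal applications from Periods 1 and 2 therefore get an abdomen review on Day 16, without a required skin finding. The 8 groin applications get neither.

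**Early withdrawal.** The exit list carried over by section 6.1.3 has no skin item. If a subject leaves before 24 hours, the 24-hour check is not assured either.

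**The case against.** A fair defence has several parts.

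- **End of study coincides with the Period 3 check.** This stands. A reader might infer that all 24 applications lose a later look, but 8 of them do not in completers.
- **The abdomen is reviewed at exit.** This stands in part. A reader might infer that the abdomen in Sequence 3 is never seen after Day 9, or that nobody looks at the abdomen of a subject who withdraws. The documents do not support that, because the exit list includes the abdomen. A general abdomen review is still not a required or documented skin check of the marked site, and it does not cover the groin.
- **Adverse events are monitored throughout.** Table 1 marks this in both wash-outs and at exit. Section 7.4 has open questions at the start of each period and before each departure, records what staff observe, and provides for follow-up if necessary. So it would be too strong to say that late reactions go unseen. A withdrawal caused by a skin reaction is also an event already detected. What remains uncovered is a planned, documented inspection of onset, persistence and resolution.
- **Supporting texts are easily over-read.** Section 6.1.3.4 has its screening counterpart in section 6.1.1.5, which concerns extra laboratory panels, so it should not be read as forbidding a skin look. The blank Visual Skin Evaluation cell under End of Study in Table 1 is also weak evidence: Vital Signs is blank there too, although section 6.1.3.1 requires them. The point rests on sections 6.1.1.2, 6.1.3.1, 6.1.3 and 6.3.3.
- **The screening skin check serves eligibility, and the document does not contradict itself.** Both are true. The asymmetry is a design choice rather than an error, and nothing in the protocol says reactions are expected to begin after 24 hours. The case for a change rests on its small cost and on the secondary objective.

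**Conclusion.** The point holds as a limited gap in the safety assessment. For 16 of 24 active applications (67%) the text assures no documented skin inspection after about 24 hours, although completers are on site 8 or 15 days after treatment. The 8 groin applications among them are the clearest case. The 8 abdominal ones are partly covered by the Day 16 abdomen review, and the 8 Period 3 applications are unaffected in completers. In early withdrawals the exit examination requires no skin check at all.

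This assumes 12 completers, the day numbers in Table 1 (a longer wash-out lengthens the intervals), and a reading of section 6.3.3 in which each check covers only the site of that period. It bears on the secondary tolerability objective only. The primary exposure objective, the pharmacokinetic parameters and the sample size are untouched. It is a cheap improvement to make, not a flaw that undermines the study.

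**What to change.** 1. Add to section 6.1.3.1 a skin examination of both application sites, abdomen and groin, mirroring section 6.1.1.2. Section 6.1.3 then carries it to discontinued subjects without further wording.
2. Mark Visual Skin Evaluation in the End of Study column of Table 1.
3. State in section 6.3.3 that the pre-treatment checks in Periods 2 and 3 also cover any site treated earlier.

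The cost is a minute or two within examinations already planned, one CRF field and one amendment line. No visit, staff or procedure is added.
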